5.8.4 ECG Results

Descriptive statistics for all reported and change from baseline values will be summarized by visit. Only the original assessment for each visit will contribute to these summaries; repeat or unscheduled assessments will not be included in the calculation of descriptive statistics. The number and percentage of participants with PCI values at any time will be tabulated by treatment group; the number and percentage of participants with abnormal ECG findings will be presented similarly. Summaries of PCI values and abnormal ECG findings will include all assessments regardless of whether an original, repeat, or unscheduled assessment. All ECG results data will be listed by study part, participant, and visit.

5.8.5 C-SSRS

The C-SSRS will be evaluated based on methods described by Nilsson et al. (2013). The number and percentage of participants with any suicidal ideation and/or suicidal behavior following the first dose of study drug will be tabulated.

For the composite endpoint of suicidal ideation, the number and percent of participants who experience any one of the five suicidal ideation events at least once during dosing through follow-up will be tabulated.

For the composite endpoint of suicidal behavior, the number and percent of participants who experience any one of the five suicidal behavior events at least once during dosing through follow-up will be tabulated.

For the composite endpoint of suicidal ideation or behavior, the number and percent of participants who experience any one of the ten suicidal ideation or behavior events at least once during dosing through follow-up will be tabulated.

5.9 Pharmacokinetic Analyses

5.9.1 Plasma Concentrations

For each study part, plasma concentrations will be summarized by visit and nominal sampling time using descriptive statistics. For concentration summaries, plasma concentrations below the level of quantification (BLQ) will be set to zero. Descriptive statistics for plasma concentrations will include n, number of participants with concentrations below the level of quantification (BLQ), mean, SD, coefficient of variation (CV%), geometric CV%, geometric mean, median, minimum, and maximum. All plasma concentration data will be listed by study part, participant, and visit.

Plasma concentrations will also be presented graphically.

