^b Vital signs include pulse rate, respiratory rate, temperature, and blood pressure. Blood pressure must be measured once after the participant has been supine for at least 5 minutes and once after the participant has been standing for at least 2 minutes. On Day 1, vital signs should be measured pre-dose, 2 hours post-dose (±30 min), and 6 hours post-dose (±30 min).

^c Including CBC, clinical chemistry, coagulation factors, viral serology screen, urinalysis, and urine albumin. Coagulation factors and viral serology screen collected at Screening only.

^d A triplicate measurement must be taken at Screening only; for all other timepoints, a single measurement is acceptable.

^e TETRAS can be completed anytime at Screening and Day 70. On other days, the following timing should be followed:

Day 1: pre-dose and 6 (±2) hours after a 20 mg QAM dose

Day 7: 6 (±2) hours after a 40 mg QAM dose

Day 21: 6 (±2) hours after an 80 mg (or highest tolerated dose) QAM dose

Day 42: pre-dose and 6 (±2) hours after a 120 mg (or highest tolerated dose) QAM dose

Day 56: 6 (±2) hours post-dose

^f The TETRAS Performance assessment will be captured on video for central reading. The local rater must rate the same TETRAS Performance assessment as that which is captured on video for central reading. The Screening video will also be independently assessed for eligibility.

^g Kinesia ONE assessments must be completed immediately after the TETRAS Performance assessments (including both pre-dose and post-dose assessments on Day 1 and Day 42). After each TETRAS Performance assessment, Kinesia ONE assessments should be completed twice separated by at least 30 minutes. All 3 maneuvers in the upper limb item (sub-items 4a, 4b, and 4c) will be completed for both arms, first for the RIGHT arm and then for the LEFT.

^h For visits with multiple TETRAS assessments, the TETRAS ADL subscale should only be assessed once. On Day 1, the ADL subscale should be completed pre-dose. On day 42, the ADL subscale should be completed 6 (±2) hours after the QAM dose.

ⁱ On Day 1 and Day 42 blood samples should be collected at the following timepoints: pre-dose and 0.5, 1, 2, 4, and 6 hours post-dose. The 6-hour post-dose sample will be collected immediately after completion of the second Kinesia ONE assessment. When PK sampling timepoints coincide with the TETRAS

Study Phase	Screening		Open-label Titration								Double-Blind Randomized Withdrawal	Safety Follow-up	

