4.1.2.2. Part B

4.1.2.2.1. Open-label Titration Phase

On Day 1, participants will receive a 20 mg dose of PRAX-944 on an empty stomach (at least 1 hour before breakfast). Participants will remain in a clinical setting under medical observation for approximately 6 hours. TETRAS Performance assessments will be performed before dosing and 6 hours (± 2) post-dose.

For dosing on Day 2 through Day 41, participants will be instructed to dose QAM at least 1 hour before breakfast at home.

Participants will continue taking PRAX-944 20 mg QAM at home through Day 3.

On Day 3, participants will receive a telephone call from site staff to inquire about AEs and concomitant medications, confirm dose escalation, and remind the participant about the number of study drug tablets to take on Day 4 through Day 7.

On Day 4, participants will escalate to 40 mg QAM through Day 7, when they will return to the clinic for safety assessments and efficacy testing. On Day 8, participants should escalate to 60 mg QAM through Day 14.

On Day 14, participants will receive a telephone call from site staff to inquire about AEs and concomitant medications, confirm dose escalation, and remind the participant about the number of study drug tablets to take on Day 15 through Day 21.

On Day 15, participants should escalate to 80 mg QAM through Day 21, when they will return to the clinic for safety assessments and efficacy testing. On Day 22, participants should escalate to 100 mg QAM through Day 28.

On Day 28, participants will receive a telephone call from site staff to inquire about AEs and concomitant medications, confirm dose escalation, and remind the participant about the number of study drug tablets to take on Day 29 through Day 42.

On Day 29, participants will escalate to 120 mg QAM through Day 42, when they will return to the clinic for safety assessments and efficacy testing. The dose on Day 42 will be taken in the clinic (see [Section 4.1.2.2.2](#) below).

On Day 35, participants will receive a telephone call from site staff to inquire about AEs and concomitant medications.

On Day 41, participants will complete a TETRAS Performance Upper Limb assessment via a telehealth visit.

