If at any point during the open-label titration phase a participant does not tolerate escalation and the Investigator returns the participant to a lower dose level, the participant will continue according to the schedule outlined above, but no further dose changes will be allowed. The Investigator should discuss the decision to continue at a lower dose level with the Sponsor and Medical Monitor. Participants can only change to a lower dose level once, and no dose changes may occur after Day 36.

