4.9.1.1 Performance subscale

The performance subscale consists of 9 items covering different body regions. Each item is rated on a scale of 0 to 4, including 0.5 increments if a rating cannot be reconciled between two whole numbers, with higher scores indicating higher tremor amplitude. Item 4 of the performance subscale is the upper limb item. It is comprised of 6 sub-items (4a, 4b, and 4c assessed for both the right and left upper limbs). The upper limb total score is the sum of these 6 items and ranges from 0 to 24. The timepoint, blinded TETRAS code, date and time of assessment, rater ID, an indicator of whether the assessment was performed (Yes/No), and the individual item scores will be recorded in the eCRF.

The full performance subscale score is calculated as the sum of item 1 (head), item 2 (face), item 3 (voice), each of the 6 sub-items for item 4 (upper limb), the maximum of the 4 sub-items for item 5 (lower limb), 2 sub-items (right and left side) for item 6 (Archimedes spirals), item 7 (handwriting), 2

sub-items (right and left side) for item 8 (dot approximation), and item 9 (standing) for a total score ranging from 0 to 64 from 16 sub-items.

The TETRAS performance subscale will be collected at the following timepoints:

Part A:

- Screening, Day 0 and Day 21: completed anytime
- Day 1: pre-dose and 6 (± 2) hours post-dose
- Day 7 and Day 14: 6 (± 2) hours post-dose

Part B:

- Screening and Day 70: completed anytime
- Day 1: pre-dose and 6 (± 2) hours after a 20 mg qAM dose
- Day 7: 6 (± 2) hours after a 40 mg qAM dose
- Day 21: 6 (± 2) hours after an 80 mg (or highest tolerated dose) qAM dose
- Day 42: pre-dose and 6 (± 2) hours after a 120 mg (or highest tolerated dose) qAM dose

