5 ANALYSIS METHODS

Analysis will be carried out using SAS® (version 9.4 or newer, SAS Institute Inc, Cary, NC). Templates for the summary tables, figures, and participant data listings will be available separately. Data listings will include all data recorded for all enrolled participants; where captured, data entered for screen failure participants will be flagged in the listings.

For all data displays, separate summaries will be generated for each part and phase (open-label titration and double-blind randomized withdrawal) of the clinical trial.

- Part A: All summaries except those for adverse events will use a single "PRAX-944 Overall" column. Summaries of adverse events will use the following columns: "PRAX-944 20 mg qAM", "PRAX-944 40 mg qAM ", and "PRAX-944 Overall".
- Part B: Summaries of disposition and PK will be presented for all of Part B (i.e., not by phase) and will use a single "PRAX-944" column.
- Part B Open-label Titration: Summaries of demographics, baseline characteristics, medical history, prior and concomitant medications, study drug exposure, efficacy, and all safety except adverse events will include a "PRAX-944 Overall" column. Summaries of adverse events will include columns for "PRAX-944 20 mg qAM", "PRAX-944 40 mg qAM ", "PRAX-944 60 mg qAM ", "PRAX-944 80 mg qAM ", "PRAX-944 100 mg qAM ", "PRAX-944 120 mg qAM ", and "PRAX-944 Overall".
- Part B Randomized Withdrawal: Summaries of demographics, baseline characteristics, medical history, prior and concomitant medications, study drug exposure, efficacy, and all safety except adverse events will include the columns "Placebo" and "PRAX-944" for the randomized withdrawal phase. Summaries of adverse events will include columns for "Placebo" and "PRAX-944".

Descriptive statistics for continuous data will include number of participants (n), mean, standard deviation (SD), median, minimum, and maximum. Summaries of change from baseline variables will include only participants who have both a baseline value and corresponding value at the timepoint of interest. Descriptive statistics for categorical data will include frequency and percentage. Where appropriate, descriptive statistics may be presented with 95% confidence intervals (CIs).

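### Part B concentrations are summarized in one PRAX-944 column, so Day 21 and Day 42 rows mix doses once anyone has stepped down, and Day 56 rows mix placebo with active

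*SAP*

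**What the plan says.** **Layout.** SAP Section 5.9.1 sets the grouping: "For each study part, plasma concentrations will be summarized by visit and nominal sampling time using descriptive statistics". The statistics include mean, SD, CV%, geometric mean and geometric CV%, and values below quantification (BLQ) are set to zero. SAP Section 5 sets the columns: "Summaries of disposition and PK will be presented for all of Part B", without division by phase and under a single PRAX-944 heading. Concentrations are also listed by part, participant and visit; dose is not named as a listed field.

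**Dose by visit.**
- Day 1 (Protocol 4.1.2.2.1): "On Day 1, participants will receive a 20 mg dose of PRAX-944 on an empty stomach". Every participant is on the same dose.
- Day 7: scheduled at 40 mg, reached on Day 4.
- Day 21 (SAP 4.9.1.1): assessments are timed in "hours after an 80 mg (or highest tolerated dose) qAM dose".
- Day 42 (Protocol Table 3, footnote e): "Day 42: pre-dose and 6 (±2) hours after a 120 mg (or highest tolerated dose) QAM dose".
- Step-down rule (Protocol 4.1.2.2.1): "Participants can only change to a lower dose level once, and no dose changes may occur after Day 36".
- Day 56: participants have been randomized 1:1 to placebo or to PRAX-944 at their existing dose.

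**Sampling.** Days 1 and 42 have samples pre-dose and at 0.5, 1, 2, 4 and 6 hours. Days 7, 21 and 56 have one sample at 2 hours (Table 3, footnote i).

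**The concern.** In Part B, visit does not fix dose after Day 1. The plan expects some participants to be below the scheduled dose at Days 21 and 42, yet the concentration table has no place to show it. Once anyone has stepped down, the row average is weighted by how many participants tolerated each level, and differences caused by dose are counted in the CV% as if they were differences between people.

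Day 42 matters most, because it is the only multi-sample profile at the top of the dose range. The stated purpose of the sample size is to inform later controlled studies, and a reader looking for exposure at 120 mg would naturally turn to that row.

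The Day 56 row has a further problem that needs no step-down. Half of the randomized participants are on placebo, and the plan gives them no column of their own.

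**Working it through.** The plan states no figure on this point, so there is none to reproduce. The check compares the layout with the dosing rules and then illustrates the size.

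**1. Is dose used elsewhere?** Yes. SAP 4.10.1 assigns adverse events to the participant's actual dose level, and SAP 5 gives those tables a column for each level from 20 to 120 mg. SAP 4.8 records date, time and dose of administration. The data for a split by dose therefore exist.

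**2. How likely are mixed doses?** The documents give no reduction rate. If each participant independently has probability p of being off the scheduled dose, the chance that at least one of n is off it is 1 − (1 − p)^n.
- n = 12: p = 10% gives 1 − 0.9^12 = 72%; p = 20% gives 1 − 0.8^12 = 93%.
- n = 24: 92% and 99.5%.

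Mixing is likely at these assumed rates but not certain.

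**3. Size at Day 42.** Assume exposure proportional to dose and the same within-dose CV, c, at every dose. With a fraction f on a lower dose and r = lower dose/120:
- pooled mean ÷ 120 mg mean: m = (1 − f) + f·r
- pooled CV = √{(1 + c²)[(1 − f) + f·r²] − m²} ÷ m

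| f | Lower dose | m | True CV | Displayed CV |
|---|---|---|---|---|
| 0 | none | 100% | 30% | 30% |
| 1/4 | 100 mg | 115/120 = 96% | 30% | 31.0% |
| 1/4 | 80 mg | 110/120 = 92% | 30% | 34.2% |
| 1/4 | 60 mg | 105/120 = 87.5% | 30% | 39.6% |
| 1/3 | 60 mg | 100/120 = 83% | 40% | 50.3% |
| 1/2 | 60 mg | 90/120 = 75% | 30% | 45.9% |

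For the fifth row: (1.16 × 0.75 − 0.694)^½ ÷ 0.833 = 0.503.

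**4. Day 56.** The last active dose for the placebo group is on Day 42, 14 days earlier. Protocol 5.4.3 equates 5 half-lives with 3 days, so 14 days is 14 ÷ 0.6 ≈ 23 half-lives. The remaining fraction is below 2^−20, about one in a million, so these samples should be BLQ and enter as zero. Under 1:1 allocation, with the active group on one dose:
- pooled mean = 0.5 × active mean
- pooled CV = √(1 + 2c²): a true 30% shows as 109%, and a true 50% as 122%
- the geometric mean on the log scale is undefined, because log(0) does not exist

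The SAP's PK analysis set (Section 3.6) does not remove these participants, since they all took PRAX-944 before randomization. Protocol 9.3 says that data from the randomized portion will be summarized by randomized continuation treatment. The single PK column departs from that, and SAP 7.1 does not list the departure.

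**The case against.** The strongest reply is that the defect is conditional and partly recoverable. Much of it stands.

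- A reader might infer that the table gives exposure at no actual dose. The documents do not support that. All Day 1 rows are at 20 mg, and any open-label visit where nobody stepped down is dose-specific.
- A reader might also infer that these rows are the trial's whole PK result, because SAP 5.9.2 drops PK parameters. That is too strong. Parameters were planned for Part A only; the protocol synopsis promises just a summary of concentrations for Part B. Part A visits have a fixed dose with no modification allowed. Individual listings and graphs are planned, and population PK and PK–efficacy analyses may follow.
- No row is labelled 120 mg, and open-label efficacy, laboratory, vital sign and ECG summaries also use one overall column. Adverse events need dose columns more, because they are not tied to visits.
- The reduction rate, CV and proportionality are all assumed. Protocol 4.3 reports that 120 mg was well tolerated in healthy volunteers after a nearly identical titration, although this does not give the rate in essential tremor.
- With about 12 participants, dose cells may hold one or two people.
- Table templates are held separately and the exploratory objectives are redacted, so the full PK presentation cannot be seen.

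The reply does not remove the point. A listing does not correct a blended summary row, the later analyses are optional, and small cells call for individual values rather than pooling. None of it answers Day 56.

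**Conclusion.** The point holds for Days 21 and 42, and possibly Day 7, on condition that at least one participant is below the scheduled dose at that visit. Those rows then describe no single dose and overstate between-participant variability. Under assumed proportionality, the worked Day 42 cases run from no distortion to a pooled mean of 75% of the 120 mg mean. These are illustrations, not predictions or bounds; half the participants on 40 mg, for example, would give (120 + 40)/2 ÷ 120 = 67%.

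At Day 56 the pooling follows from randomization itself. The mean is about half the active-arm mean, assuming 1:1 allocation, BLQ placebo samples and their inclusion in the PRAX-944 column. If the sponsor intends the column heading to exclude placebo samples, the SAP does not say so.

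This is a defect in how results are presented. It does not affect the data collected, the sample size or any hypothesis test.

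**What to change.** Amend SAP Sections 5 and 5.9.1 before database lock:

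1. Tabulate Part B concentrations within visit and nominal time by the actual dose taken on the sampling day.
2. At Day 56, tabulate by treatment received: placebo separately from PRAX-944, and PRAX-944 by dose.
3. Add dose to the concentration listing.
4. Where very few participants share a dose, show individual values instead of CV%.
5. State how geometric statistics are handled when values are set to zero.

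A dose-normalized summary for Days 21 and 42 is optional. It should state that it assumes proportionality, which the documents do not establish.

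The cost is SAP wording, extra grouping variables in the table program and a longer table. No new data are needed. The downside is small n in some dose rows, above all at Day 56: with 12 participants randomized 1:1, each arm has 6 before any split by dose.

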While the genetics and pathophysiology of ET is not fully understood, it is thought to involve abnormal activity of cerebellar afferent and efferent pathways. This network consists of input from the inferior olive to the cerebellar cortex, and outflow through deep cerebellar nuclei to the ventral thalamus and cortex. Low voltage, T-type calcium (Ca^{2+})-channels in the inferior olive and thalamus may play a role in the pathogenesis and treatment of ET. The T-type Ca^{2+} -channel family is comprised of 3 different isoforms: Cav3.1, Cav3.2, and Cav3.3. These channels are involved in generation of physiological and pathophysiological rhythms in the brain. In the harmaline rodent model of ET, synchronous neuronal discharges which are associated with T-type Ca^{2+} -channels are increased. The abnormal discharges were attenuated in mice lacking the gene that encodes for Cav3.1, and in wildtype mice, selective knockdown of Cav3.1 in the inferior olive by shRNA suppressed the harmaline-induced tremor. The non-selective Ca^{2+} channel blocker ethosuximide was found to suppress tremor in the harmaline model and in a genetic model of ET, in a dose-dependent fashion.

PRAX-944 is an orally active, small molecule that belongs to the class of T-type Ca^{2+} -channel blockers. PRAX-944 blocks all 3 T-type Ca^{2+} -channel subtypes with high potency and is therefore being studied for the treatment of ET. Different formulations of PRAX-944 have been studied in 4 single and multiple ascending dose trials in healthy volunteers. The modified-release (MR)7 formulation (80% of drug product released within 7 hours), which will be used in this trial, was well tolerated at doses of up to 120 mg per day when administered in a titration regimen.

[figure not shown]
In a human electroencephalogram (EEG)/polysomnography clinical trial, PRAX-944 showed robust suppression of the sigma frequency band during non-rapid eye movement (NREM) sleep, a marker of sleep spindle activity, at the 20 mg, 40 mg, and 60 mg dose levels. Sleep spindles are prominent oscillations of 11 to 15 Hz observed in the human scalp EEG during NREM sleep that are mediated by activation of T-type Ca^{2+} channels in the thalamus. Thus, these data suggest that PRAX-944 blocks T-type Ca^{2+} channels in the central nervous system (CNS) at well tolerated doses.

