^g To be performed 2 consecutive times separated by at least 30 minutes, the first time immediately after the post-dose TETRAS Performance assessment. All 3 maneuvers in the upper limb item (sub- items 4a, 4b, and 4c) will be completed for both arms, first for the RIGHT arm and then for the LEFT.

[figure not shown]
^h Day 1: 0 (pre-dose); post-dose immediately after completion of the 2nd accelerometer-based upper limb assessment; When PK sampling timepoints coincide with the TETRAS Performance timepoints or accelerometer-based assessment timepoints the PK sample is to be obtained last.

ⁱ Optional samples collected at sites that have capabilities to perform serial sample collection: Day 1, 7 and 14: 0 (pre-dose), 0.5, 1, 2, 3, 4, 6, 8, 10, 12, 24 hours post-dose. All collection times up to 4 hours post-dose have a ± 15 min window and a ± 30 min window thereafter. 24-hour timepoint samples are to be taken prior to the AM dose. When PK sampling timepoints coincide with the TETRAS Performance timepoints or accelerometer-based assessment timepoints the PK sample is to be obtained last.

[figure not shown]
^j Administered in clinic on Day 1. All other days it should be taken in the morning, within 30 minutes after breakfast. On Day 1 participant should be observed in clinic for approximately 6 hours before discharge. Study drug is dispensed (20 mg QAM for Day 1 to Day 7; 40 mg QAM for Day 8 to Day 14).

Schedule of Activities for Part B

Study Phase	Screening		Open-label Titration								
	Day -28 to Day -1		Day 1 (Baseline)	Day 3	Day 7	Day 14	Day 21	Day 28	Day 35	Day 41	Day 42
Visit Days (Visit Window)		Day -2 (-2)									
CLINICAL TRIAL ENTRY AND GENERAL ASSESSMENTS											
Informed Consent	X										
Inclusion/Exclusion	X		X*								
Demographic Data	X										
Medical History	X										
Body Weight/Height	X										
Drug/Alcohol Screen ^a	X		X*								
Pregnancy test	X (serum)		X (urine)*								
SAFETY ASSESSMENTS											
Vital Signs ^b	X		X		X		X				X

Study Phase	Screening		Open-label Titration								
	Day -28 to Day -1		Day 1 (Baseline)	Day 3	Day 7	Day 14	Day 21	Day 28	Day 35	Day 41	Day 42
Visit Days (Visit Window)		Day -2 (-2)									
Physical Examination	X		X*								
Clinical Laboratory Tests ^c	X		X*		X		X				X
12-lead ECG ^d	X		X*		X		X				X
C-SSRS (Baseline/Screening)	X										
C-SSRS (Since Last Visit)			X*		X		X				X

Study Phase	Screening		Open-label Titration									[REDACTED]		

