e TETRAS can be completed anytime at Screening and Day 70. On other days, the following timing should be followed: Day 1: pre-dose and 6 (±2) hours after a 20 mg QAM dose Day 7: 6 (±2) hours after a 40 mg QAM dose Day 21: 6 (±2) hours after an 80 mg (or highest tolerated dose) QAM dose Day 42: pre-dose and 6 (±2) hours after a 120 mg (or highest tolerated dose) QAM dose Day 56: 6 (±2) hours post-dose

f The TETRAS Performance assessment will be captured on video for central reading. The local rater must rate the same TETRAS Performance assessment as that which is captured on video for central reading. The Screening video will also be independently assessed for eligibility.

Study Phase	Screening		Open-label Titration									
Visit Days (Visit Window)	Day -28 to Day -1		Day 1 (Baseline)	Day 3	Day 7	Day 14	Day 21	Day 28	Day 35	Day 41		Day 42
		Day -2 (-2)										

g Kinesia ONE assessments must be completed immediately after the TETRAS Performance assessments (including both pre-dose and post-dose assessments on Day 1 and Day 42). After each TETRAS Performance assessment, Kinesia ONE assessments should be completed twice separated by at least 30 minutes. All 3 maneuvers in the upper limb item (sub-items 4a, 4b, and 4c) will be completed for both arms, first for the RIGHT arm and then for the LEFT.

h For visits with multiple TETRAS assessments, the TETRAS ADL subscale should only be assessed once. On Day 1, the ADL subscale should be completed pre-dose. On day 42, the ADL subscale should be completed 6 (±2) hours after the QAM dose.

i On Day 1 and Day 42 blood samples should be collected at the following timepoints: pre-dose and 0.5, 1, 2, 4, and 6 hours post-dose. The 6-hour post-dose sample will be collected immediately after completion of the second Kinesia ONE assessment. When PK sampling timepoints coincide with the TETRAS Performance timepoints or accelerometer-based assessment timepoints, the PK sample is to be obtained last. On Days 7, 21, and 56; samples should be collected 2 hours post-dose. Blood collection can be completed anytime on Day 70.

j Participants will be randomized (1:1) to receive either placebo or PRAX-944 from Day 43 to Day 56. Randomization can occur on Day 37 through Day 42.

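### SAP 5.9.1 sets BLQ concentrations to zero but asks for a geometric mean and geometric CV% from the same values, and zeros are expected in several scheduled rows

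*SAP*

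**What the plan says.** SAP 5.9.1 covers all concentration tables. It says that "plasma concentrations will be summarized by visit and nominal sampling time using descriptive statistics" for each study part, and gives a single BLQ rule: "For concentration summaries, plasma concentrations below the level of quantification (BLQ) will be set to zero". The statistics then listed are n, the number of participants with BLQ values, and "mean, SD, coefficient of variation (CV%), geometric CV%, geometric mean, median, minimum, and maximum". No exception, substitute value, not-calculated convention or maximum BLQ fraction follows.

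Three other places decide where the rule bites:

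- **Columns.** SAP 5 (Analysis Methods): "Summaries of disposition and PK will be presented for all of Part B (i.e., not by phase) and will use a single" PRAX-944 column.
- **Part A samples.** SAP Appendix 1, Part A schedule, footnote h: "Day 1: 0 (pre-dose); post-dose immediately after completion of the 2nd accelerometer-based upper limb assessment".
- **Part B samples.** SAP Appendix 1, Part B schedule, footnote i: "On Day 1 and Day 42 blood samples should be collected at the following timepoints: pre-dose and 0.5, 1, 2, 4, and 6" hours after the dose. The same footnote adds a 2-hour sample on Days 7, 21 and 56 and a sample at any time on Day 70.

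**The concern.** Geometric statistics are computed on the log scale, and zero has no logarithm. A programmer who follows SAP 5.9.1 literally must therefore either print 0 with an undefined CV, print nothing, or let the software omit the zeros. The last choice puts two populations in one row: n, mean, SD and median include the BLQ participants, while the geometric mean and geometric CV% do not.

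These tables carry more weight than usual here. Pharmacokinetics is in the trial title, but SAP 5.9.2 says no PK parameters will be estimated, so concentration summaries are the main PK output left in the SAP. SAP 2.3 expects the trial to inform later controlled studies.

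**Working it through.** The plan states no figure to reproduce. The check is what the rule returns, and in which rows.

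**1. The statistics with a zero present.** For n values x:

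- geometric mean = exp(mean of ln x), equivalently the n-th root of the product
- geometric CV% = 100 × √(exp(s²) − 1), where s² is the variance of ln x

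One zero among 12 values makes the product 0, so the geometric mean is 0. Because ln 0 does not exist, s² and the geometric CV% are undefined.

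**2. The statistics with zeros dropped.** With k zeros among n, the geometric mean rests on n − k values, while the row's arithmetic mean is (n − k)/n times the mean of the quantifiable values. For illustration, place the quantifiable values at the quantiles of a log-normal distribution with geometric mean 100 and CV 50% (assumed, arbitrary units):

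| n | zeros | arithmetic mean | median | geometric mean, zeros kept | geometric mean (CV%), zeros dropped | values behind it |
|---|---|---|---|---|---|---|
| 12 | 0 | 110.4 | 100.1 | 100 | 100 (49) | 12 |
| 12 | 1 | 101.1 | 94.9 | 0 | 100 (49) | 11 |
| 12 | 3 | 82.5 | 81.6 | 0 | 100 (49) | 9 |
| 12 | 6 | 54.6 | 26.0 | 0 | 100 (49) | 6 |
| 24 | 12 | 55.2 | 22.1 | 0 | 100 (49) | 12 |

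For any one set of non-negative values the geometric mean cannot exceed the arithmetic mean. From the third line on it does, which shows that the two statistics describe different participants.

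**3. Where zeros are expected.**

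- *Day 1 pre-dose, both parts.* Exclusion criterion 19 bars prior PRAX-944 exposure, so every value should be BLQ.
- *Part B Day 56, placebo arm.* Protocol 5.4.3 equates 5 half-lives with 3 days, so t½ = 72/5 = 14.4 h. The last active dose is on Day 42: 14 × 24 = 336 h, and 336/14.4 = 23.3 half-lives. The remaining fraction is 0.5^23.3 ≈ 9.5 × 10⁻⁸. If the half-life were twice as long (28.8 h), it would be 0.5^11.7 ≈ 3 × 10⁻⁴.
- *Part B Day 70.* The PRAX-944 arm is again 14 days past its last dose, so the same fraction applies. The placebo arm is 28 days past its last active dose.

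**4. The Day 56 row.** Allocation is 1:1, so about 6 of 12 (or 12 of 24) values come from placebo participants, all under a PRAX-944 heading. This is the fourth (or fifth) line of the table. The arithmetic statistics suffer too: the mean of 54.6 is about half the active level, and the median of 26.0 is the midpoint between zero and the lowest active value.

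**5. Whether another passage closes the gap.** SAP 4.11 refers to a separate PK analysis plan, but only for PK parameters. SAP 3.6 defines the PK set by dosing and sufficient data and does not remove the placebo arm or BLQ samples. SAP 7.1 is silent. Protocol 9.3 says that data from the randomized portion of Part B are summarized by randomized continuation treatment, which the single PK column does not do.

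**The case against.** Several points on the other side stand. Setting BLQ to zero is workable for the arithmetic mean, SD, median, minimum and maximum. The number of BLQ participants is printed in the same summary and every concentration is listed, so a careful reader could see what happened. Rows without a BLQ value are unaffected. Strictly, the geometric mean with a zero is computable: it is 0, and only the log-scale calculation and the geometric CV% fail. Table templates are held separately (SAP 5) and may contain a display convention that cannot be seen here. None of this tells the programmer which result to print.

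A reader might go further and infer that early absorption on active drug will be overstated by a known factor, because the tablet is modified-release ("80% of drug product released within 7 hours") and Part B samples 0.5 h after a first 20 mg dose. The documents do not support that. They give no LLOQ and no concentrations, so whether any 0.5 h value is BLQ is unknown, and the size follows from whatever is assumed. With every quantifiable value at 5, an LLOQ of 1 and 4 of 12 BLQ, dropping zeros gives 5.0, against exp((8 ln 5 + 4 ln 0.5)/12) = 2.3 with LLOQ/2. With a log-normal sample of true geometric mean 1.5 × LLOQ, CV 80% and 3 of 12 BLQ, dropping zeros gives 2.00 × LLOQ, 33% above the true value.

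A reader might also reach for LLOQ/2 substitution with suppression when more than half the values are BLQ. That fails at Day 56: exactly half is not more than half, so the pooled row would print. With six values at 5 and six at 0.5, the geometric mean is √(5 × 0.5) = 1.58 and the geometric CV about 180%, which describes neither arm.

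**Conclusion.** The point holds as a rule that fails when followed as written. Any row containing a BLQ value yields a geometric mean of 0 with an undefined geometric CV%, or two statistics resting on a smaller n than the row shows. The affected rows that can be named from the documents are Day 1 pre-dose (both parts), Part B Day 70, and Part B Day 56. Day 56 is the most misleading because placebo and active participants share one column.

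The expectation of BLQ at Days 56 and 70 rests on the 14.4 h half-life implied by the contraception text and on the scheduled 14-day gap. The concentrations in the table are assumed and show the pattern only; no fold-change is claimed. The consequence is limited to descriptive PK tables, with no effect on any efficacy or safety result.

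**What to change.** Amend SAP 5.9.1 and the Part B PK bullet in SAP 5 before database lock:

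1. Keep zero for BLQ values in the arithmetic mean, SD, CV%, median, minimum and maximum.
2. State one rule for the two geometric statistics. Either report them as not calculated at any timepoint with a BLQ value, or compute them on quantifiable values only and print that n in the row.
3. Present Part B Day 56 and Day 70 concentrations by randomized arm, in line with Protocol 9.3.

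The cost is a few lines of SAP text, one programming step and extra columns for two visits. The first option in item 2 leaves some rows without a geometric statistic, even where only one participant is BLQ. The second keeps them, but the reader must note that they describe only participants with quantifiable drug.
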